5.2.3.1 Prohibited Therapy

Uses of the following therapies are prohibited from administration in the time periods specified.

Table 1. Restricted Medications

Medication or Class of Medications	Restriction Duration (Through Week 188 Follow-Up Visit)
secukinumab (Cosentyx®), biologics targeting IL-12 except ustekinumab, IL-17 (except ixekizumab and brodalumab), and/or IL-23 directly	26 weeks prior to randomization
ustekinumab (Stelara®), Tumor Necrosis Factor (TNF)- α inhibitors except infliximab, adalimumab and etanercept	12 weeks prior to randomization
granulocyte and monocyte adsorptive apheresis (GMA)	12 weeks prior to randomization
brodalumab, ixekizumab	4 months prior to randomization
infliximab (Remicade®)	8 weeks prior to randomization
adalimumab (Humira®)	2 weeks prior to randomization
etanercept (Enbrel®) live virus vaccinations	6 weeks prior to randomization
Tofacitinib, apremilast	30 days prior to randomization
any investigational device or product (excludes psoriasis products)	30 days prior to randomization
investigational drug for psoriasis (biologics and non-biologics)	12 weeks prior to randomization, or five half-life if longer
other systemic immunomodulating treatments (e.g., methotrexate, cyclosporine A, corticosteroids, ^a cyclophosphamide)	These therapies have to be unchanged for at least 4 weeks prior to randomization, and any change in the dose should be avoided.
other systemic psoriasis treatments (e.g., retinoids, fumarates, any other drug known to possibly benefit psoriasis)	After Week 16, only dose decreasing will be permitted. Cyclosporine A and systemic corticosteroid will be tapered off after confirmation of a clinical improvement in the opinion of the investigator.
phototherapy (e.g., PUVA)	4 weeks prior to assignment
phototherapy (e.g., UVA, UVB)	2 weeks prior to assignment
topical treatment for psoriasis or any other skin condition (e.g., corticosteroids, ^b vitamin D analogues, vitamin A analogues, retinoids, salicylvaseline, salicylic acid, lactic acid, tacrolimus, tar, urea, α -hydroxy acid [fruit acids])	2 weeks prior to randomization

- a. No restriction on corticosteroids with only a topical effect (e.g., inhalative corticosteroids to treat asthma or corticosteroid drops used in the eye or ear).

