5.2.3.2 Rescue Therapy

There are no special emergency procedures to be followed.

In the event that a subject experiences an intolerable worsening of GPP or EP, as deemed by the investigator, during the course of the trial the subject will be discontinued from the trial to receive rescue treatment.

In case of adverse events in need of treatment, symptomatic therapy according to investigator judgment will be permitted. All concomitant and/or rescue therapies will be recorded on the appropriate pages of the eCRF.

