5.3.1.1 Study Procedures

Informed Consent

The subject will sign and date a study specific, Independent Ethics Committee (IEC)/Independent Review Board (IRB) approved, informed consent form before any study specific procedures are performed in order to participate in this study. Details regarding how informed consent will be obtained and documented are provided in [Section 9.3](#).

Inclusion/Exclusion Criteria

Subjects will be evaluated to ensure they meet all inclusion criteria and have none of the exclusion criteria at both the Screening and the Week 0 visit.

Demographics

The subject's demographic data, including date of birth, gender, race, ethnicity, and disease status will be collected at the Screening Visit.

Physical Examination

Complete and targeted physical examinations will be performed at visits as described in [Appendix C](#). Complete physical examination will include general appearance as well as

evaluation of all relevant organ systems. Targeted physical examination will include vital signs assessment and evaluation of organ systems associated with AE(s) symptoms or laboratory abnormalities.

Physical examination findings that are related to subject's medical history will be captured on the appropriate medical history eCRF.

Vital Signs

Vital sign assessment includes temperature, pulse rate, sitting blood pressure, and respiratory rate, after subjects have been seated comfortably for at least 5 minutes.

Measurement of vital signs should precede blood sampling and be assessed pre-dose at all dosing visits. At Visit 2 and Visit 3 additional vital signs will be taken at 5 minutes post-dose and 60 minutes post-dose.

Subjects should be closely monitored for signs and symptoms of hypersensitivity reactions for approximately 2 hours after the first dose administered and 1 hour following all other doses of study drug. Hypersensitivity reactions should be treated according to medical standards. Pre-medications for further injections might be considered and will be agreed on between investigator and AbbVie TA MD.

Body Weight and Waist Circumference

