5.3.5 Pharmacokinetic Variables

Risankizumab plasma concentrations will be determined. Descriptive statistics will be calculated for each sampling time. PK and ADA data may be combined with data from other studies and analyzed using a mixed-effects modeling approach. This analysis will estimate the population central value and the empirical Bayesian estimates of the individual values for risankizumab apparent clearance (CL/F) and volume of distribution (Vss/F). Additional parameters may be estimated if useful in the interpretation of the data. Relationships between exposure and clinical observations (efficacy or safety variables of interest) may be explored.

The number and percentage of subjects with ADA will be calculated. As appropriate, the effect of ADA on risankizumab pharmacokinetics and efficacy may be explored.

5.4 Removal of Subjects from Therapy or Assessment**5.4.1 Discontinuation of Individual Subjects**

All subjects have the right to withdraw from the study at any time without the need to justify their decision. The investigator has the right to remove subjects from the study for noncompliance, administrative or other reasons. It should be clearly understood that an excessive rate of withdrawals can render the study results uninterpretable. The sponsor reserves the right to remove any study subject from the trial for non-compliance.

An individual subject is to be withdrawn from trial treatment if:

- The subject withdraws consent for trial treatment or trial participation, without the need to justify the decision.
- The subject can no longer be treated with trial medication for other medical reasons (such as surgery, adverse events, other diseases, or pregnancy)
- Development of a toxicity or adverse event which warrants risankizumab discontinuation including but not limited to SAEs or Suspected Unexpected Serious Adverse Reactions (SUSAR)s.
- If prohibited treatment is used during the study for any indication, the subject must discontinue use of the prohibited treatment if he/she wishes to continue in the study. In case of undue safety risk for the subject, the subject should discontinue study treatment at the discretion of the investigator. If the subject received a live virus vaccination during the study, the subject must discontinue study treatment

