The following rules will be used to impute for missing data. Data imputation will be used for missing values in the efficacy analysis, but not the safety analyses.

- For continuous endpoints, LOCF (Last Observation Carried Forward) will be used to impute missing values. The LOCF will use the last observed non-missing evaluation (last completed non-missing evaluation, from composite endpoint) from the previous visit within the particular period for efficacy measures assessed to impute missing data at later visits in the same period. Baseline efficacy evaluations will not be carried forward.
- For all binary endpoints (i.e., endpoints that are either 1 (subject responded) or 0 (subject did not respond):

1. If no assessment after that visit*, then impute as failure (NRI [No Response Imputation])
2. If there are assessments at visits* before and after, only impute as success if both visits are successes; else impute as failure

Subjects that take prohibited medications to treat Psoriasis will be treated the same as those that discontinued from the trial – i.e., subsequent visits following start of prohibited medication will be considered as failure for binary endpoints.

Rounding of Numeric Results

Rounding will be performed for presentation of results. No rounding will be performed before or during analyses. The ROUND function of SAS will be used to round results.

When dichotomizing continuous variables, associated continuous variables will be rounded to 9 decimal points before applying the cutoff point to determine the response status (for example, percent change from baseline in PASI score will be rounded to 9 decimal places before comparing to 90%).

The mean and median will be rounded for presentation to 1 decimal more than the data entered into the database. The standard deviation will be rounded to 2 decimal places more than the data entered into the database. The minimum and maximum values will be presented as entered into the database.

Probabilities will be rounded to 3 decimal places before assignment of statistical significance and will be presented in rounded format. Probabilities that round to zero or are reported by SAS as zero will be presented as "< 0.001." Probabilities that round to 1 or are reported by SAS as 1 will be presented as "> 0.999."

7.0 Demographics, Baseline Characteristics, Medical History, and Previous/Concomitant Medications

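### The failure rule for prohibited medication depends on indication, so a restricted systemic drug given for another reason near Week 16 or Week 52 leaves the response counted, with no sensitivity analysis to show the effect

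*SAP*

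**What the plan says.** **Scoring rule.** SAP 6.0 states: "Subjects that take prohibited medications to treat Psoriasis will be treated the same as those that discontinued from the trial". The effect is that "subsequent visits following start of prohibited medication will be considered as failure for binary endpoints". Protocol 8.1.9 has the same rule with the same limit to psoriasis treatment.

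**Conduct rule.** Protocol 5.4.1 is wider: "If prohibited treatment is used during the study for any indication, the subject must discontinue use of the prohibited treatment if he/she wishes to continue". Such a subject can therefore stay in the study and reach the next efficacy visit.

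**Table 1 (Protocol 5.2.3.1).** For systemic immunomodulators such as methotrexate, cyclosporine A, corticosteroids and cyclophosphamide: "These therapies have to be unchanged for at least 4 weeks prior to randomization, and any change in the dose should be avoided". After Week 16 the table allows dose reductions only. The restriction names no indication. Footnote a says "No restriction on corticosteroids with only a topical effect", so systemic corticosteroid for another disease is not exempted.

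**Other treatment.** Protocol 5.2.3.2 states: "In case of adverse events in need of treatment, symptomatic therapy according to investigator judgment will be permitted". That sentence excludes no drug class.

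**Remaining SAP handling.** SAP 7.4 counts subjects who received a prohibited concomitant medication as protocol deviations, and SAP 7.3 tabulates concomitant medication. Neither is linked to response status. SAP 10.1 plans imputed and as-observed analyses, but none that varies the medication rule.

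**The concern.** A systemic corticosteroid or immunosuppressant can act on the skin, CRP or fever whatever indication is recorded. Scoring that depends on the indication can therefore let a co-medication effect count as a risankizumab response.

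Three features of the trial make this matter. It is open-label with no control group (Protocol 5.5.5.1 and 5.6.1), so the absolute proportion is the result and no comparison arm absorbs a shared bias. The GPP response can be met with no change in JDA total score plus a clinically meaningful improvement in a single component (Appendix D). The CGI-GI used for EP asks for total improvement without regard to cause (Appendix G). Where the co-medication alone produces the response, the error overstates efficacy.

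**Working it through.** The plan gives no figure to reproduce: sample size rests on feasibility and no test is planned (Protocol 8.1.3 and 8.2). The check is a reading of the rules, followed by the size of one reclassified subject.

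**1. Follow one subject through the rules.** An oral corticosteroid is started in Weeks 13 to 16 for an adverse event.
- Protocol 5.4.1: if this is prohibited treatment, it must be stopped for the subject to continue. The subject stops and continues.
- SAP 6.0 medication rule: the drug was not taken for psoriasis, so the rule does not apply.
- SAP 6.0 imputation: it fills missing values, and the Week 16 assessment is present. It enters as observed.
- SAP 7.4: the subject may be counted as a deviation; the response status stays the same.

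**2. Is the drug prohibited at all?** Before Week 16, Table 1 allows stable background use and says only that dose change should be avoided. It is therefore unclear whether a new start or an increase before the primary visit is prohibited medication for scoring, even when given for psoriasis.

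**3. Which routes reach the endpoint visits?** Doses fall at Weeks 0 and 4, then every 12 weeks: 16, 28, 40, 52.
- Treatment of a hypersensitivity reaction at an earlier dose precedes Week 16 by 16 − 0 = 16 or 16 − 4 = 12 weeks, and precedes Week 52 by at least 52 − 40 = 12 weeks.
- Protocol 5.3.1.1 says "Pre-medications for further injections might be considered", subject to agreement with the sponsor's medical director. Its timing is not given. If it is given on the day (an assumption), efficacy assessments should already be done, because Protocol 5.1 puts blood sampling last before the injection.
- Treatment of an adverse event can fall at any time. This is the main route.

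**4. Size.** Inputs: at least 8 subjects per substudy (SAP 4.3), randomized 1:1 (Protocol 5.5.3). Subjects per arm = 8/2 = 4. Shift from one reclassified responder = 1/n.

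| Group | n | Shift | All respond, exact 95% CI | One fewer, exact 95% CI |
|---|---|---|---|---|
| One dose arm | 4 | 1/4 = 25 points | 4/4 = 100% (39.8 to 100) | 3/4 = 75% (19.4 to 99.4) |
| Doses pooled | 8 | 1/8 = 12.5 points | 8/8 = 100% (63.1 to 100) | 7/8 = 87.5% (47.3 to 99.7) |

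The intervals are Clopper-Pearson: lower limit = 2.5% quantile of Beta(x, n − x + 1), upper limit = 97.5% quantile of Beta(x + 1, n − x), with upper limit 100% when x = n. SAP 10.1 plans 95% CIs without naming a method, so this choice is an assumption.

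**5. Chance that at least one subject is affected.** The documents give no frequency, so the per-subject probability q is assumed. P = 1 − (1 − q)^n.

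| q (assumed) | n = 4 | n = 8 |
|---|---|---|
| 5% | 18.5% | 33.7% |
| 10% | 34.4% | 57.0% |
| 20% | 59.0% | 83.2% |

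These are chances of such use. The chance of a wrong classification is lower, because the subject must also be someone who would not have responded without the drug.

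**The case against.** The strongest reply is that this is a choice of estimand. Protocol and SAP agree with each other, a conduct rule may be wider than a scoring rule, and the analysis is descriptive. The main source of confounding is also handled: intolerable worsening leads to discontinuation from the trial for rescue (Protocol 5.2.3.2 and 5.4.1), and visits missing after that are imputed as failure. Where use is for psoriasis and counts as prohibited, it is scored as failure.

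Much of this stands, and it limits what can be asked. A reader might infer that the primary rule is wrong and should be replaced by failure for any indication. The documents do not support that. The low response threshold also makes it likelier that an affected subject would have responded on risankizumab alone. For that subject the present rule makes no error, while a wider rule turns a true response into a failure, also worth up to 25 points.

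A reader might also take the 4 weeks in Table 1 as a ready carry-over period. It is a requirement for unchanged treatment before randomization. Other classes have their own pre-randomization intervals, from 2 weeks (adalimumab, UVA or UVB) to 26 weeks (secukinumab). Nor does anything suggest that investigators would choose a convenient indication: adverse events must be recorded in detail (Protocol 6.1) and eCRF entries need source support (Protocol 10.2).

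The reply does not remove the gap. No other section scores use for another reason as failure, and the tabulations of deviations and medications do not show whether a counted response coincided with such use.

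**Conclusion.** The gap is real and modest. Restricted systemic treatment newly started or increased for a reason other than psoriasis shortly before Week 16 or Week 52 leaves the response as observed, and the report as planned would not show how much depends on it.

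The effect is 0 to 25 percentage points per dose arm for 0 to 1 affected subject, and 12.5 points for one subject with doses pooled. This assumes 4 subjects per arm, the planned minimum; larger arms give smaller steps. The full shift is bias only if the subject would not have responded otherwise. Frequency is unknown and may be zero. The case supports a sensitivity analysis and a clearer definition beside the current rule, as an inexpensive improvement.

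**What to change.** Before database lock:

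1. **Keep the psoriasis-only rule as primary.**
2. **Add a sensitivity analysis to SAP 6.0 and 10.1** for the Week 16 and Week 52 binary endpoints. Score as failure any visit during, or within a pre-specified carry-over interval after, a new start or dose increase of a Table 1 systemic immunomodulator, systemic corticosteroid, biologic, granulocyte and monocyte apheresis or phototherapy, whatever the indication. Set the interval by drug class and label it an analysis convention.
3. **List every affected subject-visit** with agent, dates and response status under both rules.
4. **State which Table 1 starts and dose changes count as prohibited for scoring**, and reconcile Table 1, Protocol 5.4.1, Protocol 8.1.9 and SAP 6.0. This concerns scoring only; no clinical rule is proposed.

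The cost is SAP text, one extra run and one listing. An any-indication rule does not need the reason for use, but it does need dates and doses. Protocol 5.2.3 sets out those fields for psoriasis medication, while Protocol 5.2.3.2 requires other concomitant therapies to be recorded without naming fields, so confirm that the eCRF holds them. The downside is that the sensitivity rate may understate response in subjects who would have responded anyway; the report should say so.

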7.1 Demographic and Baseline Characteristics

Demographics and Baseline characteristics will be summarized for ITT population, two different treatment arms (150 mg or 75 mg) and two diseases (GPP or EP). Continuous variables will be summarized with the number of non-missing observations by mean, standard deviation, median, minimum and maximum values. Categorical data will be summarized using frequencies and percentages. No Statistical tests will be performed for this study.

The following demographic and baseline parameters will be summarized.

Subject Demographics

- Sex (male, female)
- Age (years), defined as the number of years from date of birth to date of first drug
- Age categories (< 40 years, \geq 40 – < 65 years, \geq 65 years.)
- Race (American Indian or Alaska Native, Asian, Black or African American, Native Hawaiian or Other Pacific Islander, White, Multi Race)
- Ethnicity (Hispanic or Latino, Not Hispanic or Latino)
- Body weight (kg)
- Body weight category (\leq MEDIAN kg, $>$ MEDIAN kg)
- Height (cm)
- BMI (kg/m^2)
- BMI category (< 25, \geq 25 – < 30, \geq 30)

General Baseline Characteristics

- PASI (Psoriasis Area and Severity Index)
- JDA (Japanese Dermatological Association) component scores (Mild, Moderate, Severe)

- PGA-GPP (Physician's Global Assessment of Generalized Pustular Psoriasis) (Cleared, except for residual, Minimal, Mild, Moderate, Severe, Very severe)
- DLQI (Dermatology Life Quality Index)
- BSA (Body surface area)
- C-Reactive Protein

Psoriatic Arthritis and Cardiovascular History

- Psoriatic arthritis (yes, no)
- Cardiovascular Diseases (myocardial infarction, angina pectoris, transient ischemic attack, stroke, deep vein thrombosis)
- Cardiovascular Risk Factors (hypertension, hyperlipidemia, diabetes mellitus, obesity)

General Use

- Smoking status (Current, Former, Never, Unknown)
- Alcohol status (Current, Former, Never, Unknown)

Prior Treatment

- Prior Biological Medication History (yes, no)
- Prior non-Biological Medication History (yes, no)
- Prior Psoriasis Therapy (yes, no)

Vital Signs at Baseline

- Systolic blood pressure (mmHg)
- Diastolic blood pressure (mmHg)
- Pulse (beats per minute)
- Respiratory rate (breaths per minute)
- Temperature (°C)

Clinical Tests at Screening

- Chest x-ray
- Tuberculin PPD skin test, QuantiFERON TB Gold test
- Hepatitis Testing
- Serum pregnancy test
- ECG

Immunization History

- BCG immunization
- Hepatitis B immunization

Also, Physical Exam and Pregnancy Test will be presented in listing format.

7.2 Medical History

Medical or surgical history other than psoriatic arthritis or cardiovascular diseases will be summarized using body systems and condition/diagnosis as captured on the eCRF for ITT population, two different treatment arms (150 mg or 75 mg) and two diseases (GPP or EP). The body systems will be presented in alphabetical order and the conditions/diagnoses will be presented in alphabetical order within each body system. The number and percentage of subjects with a particular condition/diagnosis will be summarized for each treatment arm and disease. Subjects reporting more than one condition/diagnosis within a body system will be counted only once for that body system. Tuberculosis history will be also summarized.

7.3 Previous Treatment and Concomitant Medications

Prior and concomitant medications will be summarized for ITT population, two different treatment arms (150 mg or 75 mg) and two diseases (GPP or EP) by generic name. A prior medication is defined as any medication taken at the time of entry into the study and prior to the first dose of risankizumab. A concomitant medication is defined as any medication that started prior to the first dose of risankizumab and continued to be

taken after the first dose of risankizumab or any medication that started after the first dose of risankizumab, but not after the last dose of study drug. The number and percentage of subjects who had taken medications will be summarized by generic drug name assigned by the World Health Organization (WHO) for both prior and concomitant medications.

7.4 Protocol Deviation

Number and percentage of subjects who reported at least one of the following protocol deviation categories will be provided in the ITT population, two different treatment arms (150 mg or 75 mg) and two diseases (GPP or EP).

- Subject entered into the study even though she/he did not satisfy entry criteria
- Subject who developed withdrawal criteria during the study and was not withdrawn
- Subject who received wrong treatment or incorrect dose
- Subject who received excluded or prohibited concomitant

8.0 Patient Disposition

The number of subjects will be tabulated by investigator site and overall. The number of subjects for each of the following categories will be summarized, for overall, two different treatment arms (150 mg or 75 mg) and two diseases (GPP or EP) in the ITT population.

- Number of subjects randomized
- Number of subjects that took at least one dose of study drug
- Number of subjects who completed at Week 28
- Number of subjects who prematurely discontinued from the study before Week 28

In addition, the number and percentage of subject who discontinued the study drug will be summarized by following categorized reason (primary and all) with frequencies and

percentages for overall, two different treatment arms (150 mg or 75 mg) and two diseases (GPP or EP) in the ITT population. Subjects with multiple reasons for premature discontinuation will be counted once in the calculation of the number and percentage of total discontinuations ("Premature Discontinuation").

- Adverse event
- Withdrew consent
- Lost to follow-up
- Others.

